1231 after at approximately 24 hours have elapsed, to take written informed consent if the patient decides to participate. The
1232 name and address of those who consent to active follow-up will be captured at this time.

1233

1234 There will be 3 different consent options:

1235

1236 A. The patient can consent to ACTIVE follow-up; where both routine data sources will be used and the patient
1237 will be actively followed up at discharge, 3 and 6 months after the index OHCA. Quality of life and mRS
1238 score will be collected at these time points.

1239

1240 B. The patient can consent to passive follow-up; with this option only routine data will be collected and the
1241 patient will not be contacted again about the study.

1242

1243 C. If a patient does not wish to be followed up they can select the option; I decline to take any further part in the
1244 study. I do not wish to be contacted again (with this option no further data collection will take place).

1245

1246 We will ask all OHCA survivors to sign the consent form, selecting which method of follow up they would prefer
1247 (three different options on the consent form). Patients will be given a copy of the consent form for their own records,
1248 one copy will be placed in the patient's medical records and the original copy will be kept in the secure study records.

1249

1250 If a patient does not wish to complete the consent form a record of this will be taken and these patients will
1251 automatically be assigned to option C where no further data collection will take place.

1252

1253 In the rare event of a patient with capacity being unable to physically complete the consent form, verbal consent will
1254 be accepted and will be documented on the study specific consent form and in the medical notes. An independent
1255 member of staff (e.g. a registered nurse caring for that patient) will be asked to annotate the consent form to indicate
1256 that they have witnessed verbal consent.

1257

1258 There will be a few cases where patients are discharged from hospital (either to another facility or their usual place of
1259 residence) before the consent process can be completed. We will post a PIL to these patients, with a covering letter,
1260 patient consent form. We will provide contact details of the local research nurse so that the patient can easily contact
1261 someone if they have any questions about the study.

1262

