1765 did. This will mostly happen if the A2 paramedic forgets to enrol the patient (and they are therefore not
1766 ‘consciously’ enrolled) or due to space issues they allow another paramedic to treat the patient. Note. If
1767 no advanced airway management was required once the enrolling paramedic arrived (e.g. because ROSC
1768 had already occurred) this is not a deviation.
- 1769 • The enrolling paramedic performed an alternative intervention to their allocation on their first advanced
1770 airway management attempt. According to the A2 protocol, enrolling paramedics should make two
1771 advanced airway management attempts with their allocated intervention before swapping to a different
1772 approach. The exception to this is solo responders in the intubation arm who are not allowed to intubate
1773 until another ambulance clinician arrives; occurrences of solo responders in the intubation arm using an i-
1774 gel before intubation will not count as a deviation but will count as a crossover in any per-protocol
1775 analyses (see section 6.2.2. for details).
- 1776 • The number of patients for whom the enrolling paramedic made only one attempt at their allocated
1777 intervention before swapping to an alternative advanced airway intervention will be noted. This is not
1778 considered a true protocol deviation as clinical reasons may have rendered a second attempt at the allocated
1779 intervention futile.

1780 The number of patients who were not ‘consciously’ enrolled in the trial will also be noted. This will often be
1781 the reason for deviations such as a patient receiving the wrong intervention, but is not a deviation in its own
1782 right.

1783 The frequency of each type of deviation will be tabulated by intervention allocation of the first A2 paramedic
1784 on scene (**Table T2 and Figure F6**). Note. It may be possible for patients to be classified as a protocol
1785 deviation for more than one reason.

1786 **3.6 Withdrawals**

1787 We have ethics approval to retain data collected up to the point of approach (after discharge from ICU) for all
1788 enrolled patients. However, patients who survive to ICU discharge and consent to participate in further data
1789 collection may later decide to withdraw. In some cases patients may be happy for data collection to continue,
1790 or for data collected up until withdrawal to be used, and therefore such patients will be included in the study

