1791 analyses on an intention to treat basis (ITT). For patients who do not wish for their previously collected data
1792 to be used, we will exclude all data collected after the point of consent (i.e. ward movements, EQ-5D and
1793 follow-up data) from any analyses.

1794 Data on all withdrawals is captured on a specific case report form (CRF), and will be tabulated by allocation
1795 of the enrolling paramedic (**Table T3**).

1796 **3.7 Analysis populations**

- 1797 • **Population 1a:** The analysis population for the primary outcome (mRS at discharge/30-days) is all
1798 patients who receive resuscitation, are attended by an A2 paramedic and meet the eligibility criteria,
1799 i.e. all trial patients. This is also the analysis population for outcome 5 (chest compression fraction),
1800 but limited to two trusts and starting partway through the trial.

- 1801
- 1802
- 1803
- **Population 1b:** The analysis population for the second component of secondary outcome 6 (ROSC on ED arrival) is all patients who receive resuscitation, are attended by an A2 paramedic, meet the eligibility criteria and were conveyed to ED.
- 1804
- 1805
- 1806
- 1807
- **Population 2:** The analysis population for secondary outcomes 1 to 4, 6 and 7 (airway management details, but only covering ROSC during advanced airway management by A2 paramedic for outcome 6) is all trial patients who received at least one advanced airway management attempt by the enrolling A2 paramedic.
- 1808
- 1809
- **Population 3:** The analysis population for secondary outcome 8 (length of initial ICU stay) is all trial patients who were admitted to ICU.
- 1810
- 1811
- 1812
- **Population 4:** The analysis population for secondary outcome 9 (length of hospital stay) is all trial patients admitted to hospital who did not refuse consent (i.e. patients who either consent to active or passive follow-up or who die prior to approach).
- 1813
- 1814
- 1815
- 1816
- 1817
- **Population 5:** The analysis population for secondary outcomes 10 and 13 (EQ-5D health scores and state scores) and secondary outcomes 11 and 12 (time to death after discharge and mRS during follow-up) is all trial patients who consent to active follow-up, survive to 30 days/hospital discharge and provide relevant data for at least one of the three time points (30 days/hospital discharge, 3 months and/or 6 months).
- 1818
- 1819
- 1820

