- **Population 0:** The population of patients who were resuscitated but did not become trial patients (either because they were not attended by an A2 paramedic or were ineligible). Characteristics of this population will be compared to those in population 1 (see **Table 1**).

1821 The primary analysis will be performed on an ITT basis, with patients grouped by the allocation of their first
1822 A2 paramedic on scene (see section 6.2.2 for details).

1823 **3.8 Safety population**

1824 The safety population is all trial patients (cf. analysis population for the primary outcome). Only serious
1825 adverse events which are unexpected and related to the intervention are collected, so numbers are expected to
1826 be low. These will be presented along with all intervention details.

1827

1828 **4. DATA SOURCES**

1829 A number of variables collected in AIRWAY-2 are recorded in more than one place. The following table details
 1830 these variables and identifies the primary data sources and the order in which data will be selected; for example
 1831 gender will be taken from Form G2, if not available from Form G2 then Form G will be used, if not available
 1832 from Form G then Form E1 will be used and if not available from Form E1 then Form B will be used.

Variable	Data sources	Order of preference
Date and time of incident	Form A (CAD) Form E1 (paramedic)	Always use form A as this should be available for all patients
Gender	Form B (minimal dataset/CAD) Form E1 (paramedic) Form G (hospital details, only available for those surviving to hospital admission)	1. Form G2 2. Form G 3. Form E1 4. Form B
Date of birth (DOB)	Form B (minimal dataset/CAD) Form E1 (paramedic) Form G (hospital details, only available for those surviving to hospital admission)	1. Form G2 2. Form G 3. Form E1 4. Form B
Approximate age (Note. This variable will only be used if the date of birth is missing from all sources. If date of birth is recorded, age will be derived (see Section 5))	For patients who do not survive to hospital, age may be estimated on scene. If this is the case, this will be recorded on Form B (minimal dataset/CAD) Form E1 (paramedic)	1. Form E1 2. Form B
Presenting rhythm	Form B (minimal dataset/CAD) Form E1 (paramedic)	1. Form E1 2. Form B
Was event witnessed?	Form B (minimal dataset/CAD) Form E1 (paramedic)	1. Form E1 2. Form B
Who was the event witnessed by?	Form B (minimal dataset/CAD) Form E1 (paramedic)	1. Form E1 2. Form B

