1873 quartile range (IQR) if the distribution is skewed), and categorical data will be summarised as a number and
1874 percentage. The summary statistic headings given in **Tables T4** and **T5** are those we expect to use based on a-
1875 priori knowledge of the clinical measurements gained from previous studies. However, if distributional
1876 assumptions are not satisfied, changes will be made.

1877 Statistical tests to compare data not listed as outcomes will not be performed. Secondary outcomes 4
1878 (sequence of airway interventions delivered) and 7 (airway management in place when ROSC was achieved
1879 or resuscitation discontinued) will be described but not formally compared.

1880 **6.2 Primary and secondary outcome data**

1881 **6.2.1 Adjustment in models**

1882 The intention is to adjust the models for the three stratification (design) factors: ambulance trust (four levels),
1883 clinical experience (two levels) and the location of the paramedic’s base ambulance station (two levels) as
1884 fixed effects, and paramedic as a random effect (or a shared frailty term in the time to event model). For the
1885 mRS model where the majority of patients will have a poor outcome/death, the data may be insufficient to
1886 allow estimation of regression coefficients for all these variables. If this is the case, inestimable stratification
1887 variables will be dropped from the model and will be noted in a footnote. For the time to death model, if a cox
1888 model is used the analysis will be stratified by trust (to allow for varying baseline hazards) and adjusted for
1889 the other design factors. If either of the design factors do not meet the proportional hazards assumptions,
1890 stratification by these factors will also be implemented.

1891 **6.2.2 Data presentation and analysis models**

1892 For intention to treat analyses, data will be presented and analysed by the allocated group of the first A2
1893 paramedic on scene, regardless of what airway management the patient received. For per-protocol analyses
1894 (see sections 6.2.5 and 6.2.6), data will be presented and analysed by the allocation of the first advanced
1895 airway management used; if neither i-gel nor intubation was used (or if another SGA was used before an i-gel
1896 or intubation), the patients will be excluded from per-protocol analyses.

1897 All analyses and data presentation will be by intention to treat unless otherwise stated in the Table heading.

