Duration of ICU stay in all patients admitted to ICU from ED (hours; median, IQR)

HOSPITAL STAY

Survived to hospital discharge
Duration of hospital stay in patients who survived to discharge (days; median, IQR)
Duration of hospital stay in patients who died before discharge (hours; median, IQR)
Duration of hospital stay in all patients admitted to ED (hours; median, IQR)

2075
2076
2077
2078
2079

¹OR=Odds ratio (from logistic or, where marked *, multinomial regression), MD=mean difference, GMR=Geometric mean ratio

[figure not shown]
Table T8 Longitudinal secondary outcomes

	Randomised to intubation (n=XX)		Randomised to i-gel (n=XX)		Overall (n=XX)	
	n	%	n	%	N	%
mRS (0 to 3; good recovery)						
Discharge/30 days						
3 months						
6 months						
Treatment*time interaction						
Overall						OR
	Randomised to intubation (n=XX)		Randomised to i-gel (n=XX)		Overall (n=XX)	
	n	%	n	%	N	%
EQ5D index score (median, IQR)						
Discharge/30 days						
3 months						
6 months						
Treatment*time interaction						
Overall						OR, GMR
EQ5D visual analogue scale score (median, IQR)						
Discharge/30 days						
3 months						
6 months						

Treatment*time interaction	
Overall	OR, GMR

2080
2081
2082
2083
2084
2085
2086
2087

Figure F7 Subgroup analyses (example for one subgroup analysis: event witnessed by ambulance staff)

2088
2089

Table T9 Unexpected serious adverse events

		Received Intubation first (n=XX)		Received i-gel first (n=XX)	
		n	%	n	%
Number of patients experiencing one or more SAEs					
Number of events					
Brief description of events					
Timing of events	Pre-surgery Post-surgery but pre-discharge Post-discharge				
Maximum intensity	Mild Moderate Severe				
Reason event classified as SAE	Resulted in death Is/was life threatening Resulted in persistent or significant disability/incapacity Prolonged ongoing hospitalisation/ caused hospitalisation Other				
Relatedness to intervention	Possibly related Probably related Definitely related				

2090
2091
2092
2093

Table T10 Details of unexpected serious adverse events

Study ID=	Intervention randomised to=	Interventions received=	Patient withdrawn from study (and when)=
OHCA date=	Hospital discharge date (if applicable)=	Death date (if applicable)=	Timing of SAE= Post-intervention but pre-discharge/ Post-discharge
Brief description of event=	Location=	Maximum intensity=	Relatedness=
SAE start date/time=	SAE resolution date/time=	Event resulted in death=	Event was life threatening=

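### The only SAE summary (SAP Table T9) groups patients by device received first, so it neither covers the stated safety population nor shows SAEs by randomised group

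*Protocol*

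**What the plan says.** - **Who is in the safety population.** SAP section 3.8: "The safety population is all trial patients (cf. analysis population for the primary outcome". That population (1a, SAP section 3.7) is all "patients who receive resuscitation, are attended by an A2 paramedic and meet the eligibility criteria". Membership does not depend on any airway device having been used.
- **How tables are grouped.** SAP section 6.2.2: "All analyses and data presentation will be by intention to treat unless otherwise stated in the Table heading". The same section defines intention to treat by the allocation of the first AIRWAYS-2 (A2) paramedic on scene.
- **What the SAE summary shows.** Table T9 in Appendix A has two columns, "Received Intubation first (n=XX" and "Received i-gel first (n=XX". There is no third column and no overall column. The table title does not mention the grouping.
- **Patients who fit neither column are foreseen.** Section 6.2.2 removes patients from per-protocol analyses "if neither i-gel nor intubation was used (or if another SGA was used before an i-gel" or intubation. The notes to Figures F1 and F6 also expect patients who received only another supraglottic device (SGA).
- **Crossover is foreseen.** SAP section 3.5 says that solo responders in the intubation arm may not intubate "until another ambulance clinician arrives; occurrences of solo responders in the intubation arm using an i"-gel before intubation are then not counted as deviations.
- **What limits the matter.** SAP sections 3.8 and 6.3 restrict collection to SAEs that are unexpected and related (in 6.3, potentially related) to the intervention, and section 6.3 plans no formal comparison. Table T10 lists each SAE with the randomised intervention and the interventions received.
- **Follow-up.** Protocol section 8.4 extends adverse event collection through the 6-month follow-up without exception. Under section 9.7.1, a patient choosing option C declines any further part in the "study. I do not wish to be contacted again (with this option no further data collection will take place".

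**The concern.** The trial compares two strategies, assigned by randomising paramedics, and the safety population is declared to be everyone enrolled. A reader of the trial report would expect the SAE summary to show events and patients at risk in each randomised arm. T9 cannot supply this. Its denominators leave out some enrolled patients, and its columns are defined by something that happened after allocation. The first device used can depend on who was present and on the state of the patient and the scene, so the columns are not the randomised groups.

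What is at stake is whether the published SAE table answers the question that the design was built to answer, and whether its denominators agree with the stated population. No efficacy estimate or test depends on it.

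**Working it through.** The plan gives no figure to reproduce here, so the check sets the passages against each other.

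**1. Coverage.** Sort all trial patients, N, by first advanced device: intubation (a), i-gel (b), another SGA (c), none or not recorded (d). Then N = a + b + c + d. T9's denominators are a and b, so they fall short of the section 3.8 population by c + d. The plan expects both to be above zero:
- c: section 6.2.2 and the notes to Figures F1 and F6 provide for other SGAs.
- d: section 3.5 describes patients who need no advanced airway because circulation has already returned. Section 3.7 makes Population 2 (at least one advanced attempt by the enrolling paramedic) a separate population from 1a. Table T5 has rows for no reported attempt, including one for details that the paramedic cannot recall.

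Section 6.2.2 authorises leaving such patients out of per-protocol analyses only. Nothing extends that to safety.

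**2. Grouping.** Split each class by allocation, T for the intubation arm and I for the i-gel arm. The randomised intubation arm is a_T + b_T + c_T + d_T. T9 reports only a = a_T + a_I and b = b_T + b_I, from which neither arm can be recovered. The solo-responder exemption makes b_T positive by design. The derivation of protocol deviation 4 (SAP section 5.4) allows for a_I as well. An intubation-arm patient who is given an i-gel first and intubated later sits in the i-gel column, even for an event caused by the later intubation.

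**3. Does T9 state an exception?** Tables T2 to T8 all use columns headed by randomised group. T9's title states no exception to intention to treat; its column heads show a different grouping. Whether column heads count as the table heading in section 6.2.2 is open. Sections 3.8 and 6.3 neither announce nor explain the change.

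**4. Are events lost?** No. Section 6.3 promises full details of every event, and T10 records both allocation and treatment received. T10 is a listing, though, so it gives no denominators by arm.

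**5. Size.** The documents give no count or share for c, d, b_T or a_I, so no number is put on the shortfall. The planned 4,535 per group describes randomised groups and is not a T9 denominator.

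**6. SAE collection period.** Section 8.4 runs to 6 months for participants generally. Section 5.5 ends the trial at approach for option C and for those who do not respond. Section 9.7.1 says that no further data are collected for either. As worded, 8.4 promises data that the other two sections rule out.

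**The case against.** The best defence is that T9 is a deliberate as-treated display. Reportable SAEs must be potentially related to the intervention (Protocol section 8.3), and an injury caused by an i-gel is most informative under i-gel, whatever the allocation. The column heads say what the grouping is, and Appendix A is a guide whose layout may change. Much of this stands. By-device display of device-related events is legitimate and should be kept. What does not stand is that it should be the only summary, unannounced in the text and with part of the safety population outside it. Appendix A may change in layout, but SAP section 1.4 asks that content stay consistent with it. T9's timing rows also refer to surgery, which this trial does not involve, so the layout may not have been considered closely.

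The defence is also right that a patient with no advanced airway attempt is unlikely to have a device-related SAE. The realistic gap in events is patients given another SGA. For the rest, the gap is in denominators.

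A reader might infer that SAEs vanish from the report, or that the layout systematically loads events onto i-gel. The documents support neither. T10 lists every event, and although the solo-responder exemption runs in one direction, the plan also foresees i-gel-arm patients who are intubated first.

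**Conclusion.** The point holds in a limited form. As written, T9 does not cover the section 3.8 safety population and does not present SAEs by randomised group, the default under section 6.2.2. This assumes only that some trial patients receive neither device first and that some cross over, both of which the plan expects.

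Two further inferences should not be drawn. First, the by-device grouping does not itself breach section 3.8, which fixes who is included and not how they are grouped; the relevant text is section 6.2.2. Second, a reader might suppose that the post-discharge row dilutes event rates by dividing by whole arms. T9 does not say what denominator its timing rows use, so this cannot be shown.

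The consequence is modest: few events are expected, no test is planned and the listing is complete. It is a reporting mismatch worth correcting, and it affects no estimate. The conflict between section 8.4 and sections 5.5 and 9.7.1 is a secondary point of wording.

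**What to change.** 1. In T9, present SAEs by allocation of the first A2 paramedic on scene, with all trial patients in each arm as denominators.
2. Keep the by-first-device table as a second view. Say in its title that it is grouped by first device received, and add a column for other SGA or neither, so that the columns sum to the safety population.
3. Add a sentence to SAP section 3.8 or 6.3 naming both presentations.
4. Reconcile Protocol section 8.4 with sections 5.5 and 9.7.1, so that the SAE collection period is stated consistently for option C patients and non-responders.

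The cost is a table layout and a few sentences. Allocation and interventions received are already to be recorded for every SAE in T10, and allocation is known for every trial patient, so no new data are needed and the by-device information is kept.

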APPENDIX B: INDIVIDUAL EQ5D QUESTION DATA

		Randomised to Intubation (n=XX)		Randomised to i-gel (n=XX)		Overall (n=XX)	
		n	%	n	%	n	%
MOBILITY							
Discharge/30 days	No problems walking about						
	Slight problems walking about						
	Moderate problems walking about						
	Severe problems walking about						
	Unable to walk about						
3 months	No problems walking about						
	Slight problems walking about						
	Moderate problems walking about						
	Severe problems walking about						
	Unable to walk about						
6 months	No problems walking about						
	Slight problems walking about						
	Moderate problems walking about						
	Severe problems walking about						
	Unable to walk about						
SELF-CARE							
Discharge/30 days	No problems with washing or dressing						
	Slight problems washing or dressing						
	Moderate problems washing or dressing						
	Severe problems washing or dressing						
	Unable to wash or dress						
3 months	No problems with washing or dressing						
	Slight problems washing or dressing						
	Moderate problems washing or dressing						
	Severe problems washing or dressing						
	Unable to wash or dress						
6 months	No problems with washing or dressing						
	Slight problems washing or dressing						
	Moderate problems washing or dressing						

	Severe problems washing or dressing Unable to wash or dress						
USUAL ACTIVITIES							
Discharge/30 days	No problems with usual activities Slight problems with usual activities Moderate problems with usual activities Severe problems with usual activities Unable to perform usual activities						
3 months	No problems with usual activities Slight problems with usual activities Moderate problems with usual activities Severe problems with usual activities Unable to perform usual activities						
6 months	No problems with usual activities Slight problems with usual activities Moderate problems with usual activities Severe problems with usual activities Unable to perform usual activities						
PAIN/DISCOMFORT							
Baseline	No pain or discomfort Slight pain or discomfort Moderate pain or discomfort Severe pain or discomfort Extreme pain or discomfort						
3 months	No pain or discomfort Slight pain or discomfort Moderate pain or discomfort Severe pain or discomfort Extreme pain or discomfort						
6 months	No pain or discomfort Slight pain or discomfort Moderate pain or discomfort Severe pain or discomfort Extreme pain or discomfort						
ANXIETY/DEPRESSION							
Baseline	Not anxious or depressed						

3 months	Slightly anxious or depressed					
	Moderately anxious or depressed					
	Severely anxious or depressed					
	Extremely anxious or depressed					
	Not anxious or depressed					
6 months	Slightly anxious or depressed					
	Moderately anxious or depressed					
	Severely anxious or depressed					
	Extremely anxious or depressed					
	Not anxious or depressed					
	Slightly anxious or depressed					
	Moderately anxious or depressed					
	Severely anxious or depressed					
	Extremely anxious or depressed					

2099
2100
2101
